7.2.3 Observed Cases Analysis

A sensitivity analysis will be performed for both co-primary endpoints based on the FAS, observed cases population. For each co-primary endpoint, the observed cases population is defined to include all subjects who have an observed value for that endpoint, irrespective of an intercurrent event, and the observed value is used in the analysis. For both co-primary endpoints, the estimator and estimation methods are the same as described in Section 7.1.5, with the exception that in the observed cases population there are no missing data; consequently, no imputation is required.

7.2.4 Tipping Point Analysis

If the analyses of both co-primary endpoints are statistically significant, then an additional sensitivity analysis of the primary estimand will be performed to determine the smallest constant, δ , applied to the imputed missing data in the active treatment groups, that will yield a mean treatment difference such that the result using the primary analysis model described in Section 7.1.5 is no longer statistically significant. The constant δ represents a worsening of treatment values and the smallest value, say δ^* , that yields a non-significant result for the primary analysis is called the “Tipping Point.”

For the co-primary APOV endpoint, a worsening of treatment values means that APOV values in the active treatment groups would increase at Week 24/ET; therefore, $\delta > 0$. The value δ^* provides a measure of the robustness of the primary analysis result. The larger the value of δ^* the more robust are the results of the primary analysis to the impact of missing data, and, conversely, the smaller the value of δ^* the more sensitive the results of the primary analysis are to missing data. Ultimately however, a Tipping Point analysis is a numerical search procedure. A value of the Tipping Point, if reached, needs to be interpreted in the context of its clinical plausibility.

For the treatment policy estimand, (reference Section 7.1.3, criteria 3, c), missing data due to study discontinuation for APOV endpoint will be imputed under MAR assumption in both active treatment and placebo groups, then the constant δ is applied (added) to the imputed values in the active treatment groups. Further detail on the implementation is provided in Section 10.

For the CSNS co-primary endpoint, it is anticipated that there will be an insufficient number of early study discontinuations (discontinuations prior to Week 4) to warrant a formal Tipping Point analysis. If this is not the case, then a Tipping Point analysis will be performed for the CSNS co-primary endpoint using the same approach as described above.

7.3 Estimation - Key Secondary Efficacy Endpoints

The following key secondary endpoints (defined in Section 3.4.2) are included in the strategy for strong control of the Type I error probability in the trial. For the key secondary endpoints, intercurrent events will be addressed as described in Section 7.1.3 for the primary estimand.

The analyses of these key secondary endpoints are defined by pooling the data from Study OPN-FLU-CS-3205 and Study OPN-FLU-CS-3206.

7.3.1 CSNS in Subjects on INS at Baseline – Pooled Analysis

Change from baseline to Week 4 in CSNS in subjects who were symptomatic at trial entry despite reported use of an intranasal steroid (INS) for treatment of CRS within 30 days of Visit 1 will be analyzed using the same MMRM model described for the co-primary endpoint CSNS and the model will include a categorical effect term for protocol (CS-3205, CS-3206).

7.3.2 Acute CRS Exacerbations – Pooled Analysis

How an acute CRS exacerbation is defined and captured in this study is described in Section 9.3.5. The frequency of acute sinus exacerbations over 24 weeks will be compared between OPN-375

dose groups and placebo using generalized linear model (GLM) for data from the negative binomial distribution that is commonly referred to as the negative binomial (NB) regression model. The NB model will include the same model terms as the primary models; in addition, the model will include a categorical effect for protocol (CS-3205, CS-3206), and the logarithm of exposure time as an offset variable.

Regarding intercurrent events, use of systemic corticosteroids is included in the definition of acute exacerbation; subjects who have surgery or study discontinuation events will be censored at the time of the intercurrent event. Subjects who discontinue treatment are followed to study completion or intercurrent event as described in Section 7.1.3.

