## 4 SELECTION AND WITHDRAWAL OF SUBJECTS

### 4.1 Inclusion Criteria

Potential subjects must meet the following criteria to enter this study:

1. men or women aged 18 years and older at baseline visit
2. women of child bearing potential must be abstinent, or if sexually active:
  - a. be practicing an effective method of birth control (eg, prescription oral contraceptives, contraceptive injections, contraceptive patch, intrauterine device, double-barrier method [eg, condoms, diaphragm, or cervical cap with spermicidal foam, cream, or gel], or male partner sterilization) before entry and throughout the study, or
  - b. be surgically sterile (have had a hysterectomy or bilateral oophorectomy, tubal ligation, or otherwise be incapable of pregnancy), or
  - c. be postmenopausal (amenorrhea for at least 1 year).
3. women of child-bearing potential must have a negative urine pregnancy test at Visit 1 (Screening)
4. must have a history of CRS and be currently experiencing 2 or more of the following symptoms, one of which has to be either nasal congestion or nasal discharge (anterior and/or posterior nasal discharge) for equal to or greater than 12 weeks:
  - nasal congestion
  - nasal discharge (anterior and/or posterior nasal discharge)
  - facial pain or pressure
  - reduction or loss of smell
5. endoscopic evidence of nasal mucosal disease, with edema, purulent discharge, or polyps in middle meatus, bilaterally, or presence of bilateral disease on a prior CT scan performed within 14 days of Visit 1
6. must have confirmatory evidence via CT of bilateral sinus disease (have at least 1 sinus on each side of nose with a Lund-Mackay score of  $\geq 1$ )
7. baseline CT scan must show a combined  $\geq 25\%$  opacification of the ethmoid sinuses and  $\geq 25\%$  opacification of at least 1 maxillary sinus
8. must have at least moderate symptoms (as defined in [Section 7.2](#)) of nasal congestion as reported by the subject, on average, for the 7-day period preceding Visit 1 (Screening) run-in
9. must have an average morning score of at least 1.5 for congestion on the Nasal Symptom Scale (as defined in [Section 7.2](#)) recorded on the subject diary over a 7-day period during the first 14 days of the single-blind run-in period
10. must demonstrate an ability to correctly complete the daily diary during the run-in period to be eligible for randomization

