#### 7.1.2 Information Pertaining to Chronic Rhinosinusitis

Information pertaining to the subject's CRS, including date of initial diagnosis, number of exacerbations in the previous year, prior treatments for the condition (eg, surgery, medication) will be collected.

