6.4 CRS History

Information pertaining to subjects’ chronic sinusitis history will be summarized.

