7.1.5 Estimator and Estimation Method - Primary Efficacy Analysis

Estimator and estimation method (CSNS): For the co-primary endpoint CSNS, the estimator is the mean difference between treatments (active versus placebo) in change from baseline to the end of Week 4 in the 7-day average instantaneous AM CSNS. Estimation is based on a mixed-effects model for repeated measures (MMRM) where changes from baseline to Week 2 and Week 4, in the 7-day average instantaneous AM CSNS, respectively, are the repeated measures. The 7-day windows used to define the 7-day average instantaneous AM CSNS from baseline through Day 84 (Week 12) are provided in Section 9.1.2.1, Table 9.1. The MMRM model will employ Restricted Maximum Likelihood (REML) for parameter estimation and the Kenward-Roger method for calculating the denominator degrees of freedom. An unstructured covariance matrix will be used to estimate within-subject error. For the treatment policy estimand, (reference Section 7.1.3, criteria 3,c), missing data due to study discontinuation will be estimated within the MMRM model under the assumption that the missing data are missing at random (MAR) and that early discontinuation from the study (prior to Week 4) is unlikely to reflect a treatment effect. Contingencies in the event of an issue with MMRM model convergence are described in Section 10.5.

The MMRM model will include categorical effects for previous sinus surgery (Y,N), nasal polyp status (present, absent), treatment (OPN-375 186 µg, OPN-375 372 µg, placebo), Week (2, 4), treatment-by-day interaction, and the continuous covariate: baseline 7-day average total instantaneous AM CSNS, with baseline-by-day interaction. The model-based LS mean difference between each active treatment group and placebo (active-placebo), 95% CI, and p-value will be displayed.

Estimator and estimation method (APOV): For the co-primary endpoint APOV, the estimator is the mean difference between treatments (active versus placebo) in the change from baseline to Week 24/ET APOV. Estimation is based on an ANCOVA model including categorical effects for previous sinus surgery (Y, N), nasal polyp status (present, absent), treatment (OPN-375 186 µg, OPN-375 372 µg, placebo), and baseline APOV. The model-based LS mean difference between each active treatment group and placebo (active-placebo), 95% CI, and p-value will be displayed.

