7.5 Estimation - Other Secondary Efficacy Endpoints

All statistical analyses in this section that reference the primary MMRM and ANCOVA models described in Section 7.1.5 will include the same factors as their respective primary models, except for the baseline covariate. The baseline covariate for the specific endpoint described in this section will be used, unless otherwise specified.

In addition, a combined dose group (OPN-375 186 μ g, OPN-375 372 μ g) is defined in all models of primary and secondary endpoints by including appropriate contrasts, assigning equal weight to each dose, to obtain the inferential statistics for combined doses and for the comparison: combined doses versus placebo.

Intercurrent events for secondary endpoints will be addressed as described in Section 7.1.3 for the primary estimand, unless otherwise indicated. For the treatment policy estimand, (reference Section 7.1.3, criteria 3,c), missing data due to study discontinuation will be handled as described in Section 7.1.5 for the primary MMRM and ANCOVA models, respectively. Further details on the MI method for endpoints based on the ANCOVA model are described in Section 10.

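### The alpha-controlled exacerbation-rate model leaves out the prior-year exacerbation count collected at screening; what is at stake is precision, not validity

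*SAP*

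**What the plan says.** SAP 7.3.2 analyses exacerbation frequency, pooled over Studies 3205 and 3206, by negative binomial (NB) regression: "The NB model will include the same model terms as the primary models; in addition, the model will include a categorical effect for protocol", together with "the logarithm of exposure time as an offset variable". Protocol 9.5 and the protocol synopsis specify the same model.

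The inherited terms are in SAP 7.1.5. For APOV: "Estimation is based on an ANCOVA model including categorical effects for previous sinus surgery (Y, N), nasal polyp status (present, absent), treatment", and baseline APOV. The CSNS model has the same factors plus week, interactions and "the continuous covariate: baseline 7-day average total instantaneous AM CSNS". Neither contains a term for exacerbation history.

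Protocol 7.1.2 collects the "number of exacerbations in the previous year", and the schedule places CRS history at Visit 1, before randomization. The only use the SAP states for this history is in 6.4: "chronic sinusitis history will be summarized".

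Entry rests on symptoms, endoscopy or CT findings and a congestion score. Inclusion criterion 4 begins "must have a history of CRS and be currently experiencing 2 or more of the following symptoms", and no criterion asks for a past exacerbation. Exclusion criterion 18 screens out only unresolved or recent infection.

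Under SAP 7.4.1 the two exacerbation comparisons are third and fourth of the four key secondary tests in the alpha-controlled sequence.

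**The concern.** Subjects not selected on exacerbation history may differ widely in how often they exacerbate, and follow-up is only 24 weeks. If the tendency persists within a subject, the prior-year count explains part of the between-subject variation that the NB model otherwise carries as dispersion. Leaving it out would then give a less precise rate ratio and no adjustment for a chance imbalance in history between arms. The endpoint is confirmatory, and the covariate has to be named before unblinding to be credible.

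**Working it through.** **The plan's own power figures.** SAP 4.2 states power only for the co-primary endpoints: 88% with 111 per group, two-sided 5%. The normal approximation is power = Φ(d / (SD·√(2/n)) − 1.96).

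- CSNS: 0.8 / (1.9 × √(2/111)) = 3.137, giving 88.0%.
- APOV: 11.3 / (27 × √(2/111)) = 3.118, giving 87.7%.

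Both agree with the stated 88%. No rate, dispersion or power is stated for exacerbations, so the rest is conditional on assumptions.

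**Assumed inputs.** Placebo rate μ₀ of 0.1 to 0.8 events per 24 weeks; NB dispersion k of 0.5 to 2; rate ratio 0.6; 111 per group (this study's planned size) or 185 per group. The 185 is an assumed pooled size, because the size of Study 3206 is not given.

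**Formulas.**

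- Var(log RR) = S/n, with S = 1/μ₀ + 1/(0.6μ₀) + 2k.
- Prior-year mean m = μ₀ × 52/24.
- If each subject's underlying rate is fully stable (gamma-Poisson), conditioning on the prior count leaves average residual dispersion k_r = 1/(1/k + m).
- Half persistence is taken as removing half of k − k_r.

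| μ₀ | k | m | k_r | S without count | S with count (full) | Variance cut, half to full |
|---|---|---|---|---|---|---|
| 0.1 | 0.5 | 0.22 | 0.45 | 27.67 | 27.57 | 0.2% to 0.4% |
| 0.2 | 1 | 0.43 | 0.70 | 15.33 | 14.73 | 2% to 4% |
| 0.4 | 1 | 0.87 | 0.54 | 8.67 | 7.74 | 5% to 11% |
| 0.8 | 1 | 1.73 | 0.37 | 5.33 | 4.07 | 12% to 24% |
| 0.8 | 2 | 1.73 | 0.45 | 7.33 | 4.23 | 21% to 42% |

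Example, third row: S = 2.5 + 4.167 + 2 = 8.667. With the count at full persistence, 2k_r = 1.071 replaces 2, so S = 7.738. The cut is 0.929/8.667 = 10.7%.

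**Power**, from Φ(|log 0.6| / √(S/n) − 1.96) with k = 1, going from no covariate to half and full persistence:

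| μ₀ | 111 per group | 185 per group |
|---|---|---|
| 0.2 | 28% to 28–29% | 43% to 43–44% |
| 0.4 | 45% to 47–49% | 66% to 68–71% |
| 0.8 | 64% to 70–76% | 85% to 89–93% |

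**Simulation check.** NB regressions were fitted with and without log(prior count + 0.5), 400 runs per scenario. With 111 per group, k = 1 and full persistence, the median standard error of log RR fell as follows:

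- μ₀ = 0.2: from 0.380 to 0.375, a variance cut of 1 − (0.375/0.380)² = 2.6%.
- μ₀ = 0.4: from 0.282 to 0.270, a cut of 8.3%.
- μ₀ = 0.8: from 0.218 to 0.192, a cut of 22.4%.

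These lie slightly below the formula. The half-persistence runs gained less than the formula: 0.283 to 0.280 (2.1%) at 0.4 and 0.221 to 0.214 (6.2%) at 0.8. The formula's figures are therefore not conservative.

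Under the null at 185 per group, rejection was 2.9% to 6.0% without the count and 3.1% to 7.1% with it. Monte Carlo error is about 1.1 points, so neither model shows loss of type I error control. Up to 13% of runs in a scenario were dropped for non-convergence.

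**The case against.** The strongest reply is that this is optional efficiency. Randomization is stratified by polyp status and prior surgery, both are in the model, and the dispersion parameter absorbs the remaining variation in rates. The test is valid as written, and CRS history is tabulated by arm, so an imbalance would be visible. All of that stands. It limits the point to precision and does not remove it.

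The count may also be a poor match for the endpoint. Protocol 7.1.2 does not define it, whereas the trial event (Protocol 7.2, SAP 9.3.5) needs at least 3 days of worsening, medical care sought, treatment escalation and a 7-day merging rule. Background treatment also changes, because intranasal steroids stop at screening. This stands too: predictive value is assumed, not documented.

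A reader might infer several stronger things that the documents do not support:

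- **That the SAP breaks its own rule.** SAP 7.5 says "The baseline covariate for the specific endpoint described in this section will be used, unless otherwise specified". That rule covers the other secondary endpoints analysed with the primary MMRM and ANCOVA models, not the NB model in 7.3.2. Even within 7.5, the PGIC model has no baseline covariate, and the log-rank test of time to first exacerbation uses only the two stratification factors. The rule is an analogy at most.
- **That the gain could be half the variance.** An idealised gamma-Poisson calculation reaches 52% at 2 prior-year events and dispersion 2. It assumes full persistence and subject-specific posterior means and dispersions, which a simple covariate in a standard NB model does not deliver.
- **That baseline CSNS or APOV should be dropped in exchange.** Nothing shows that they lack prognostic value. What can be shown is that SAP 7.3.2 refers to primary models in the plural, their baselines differ, and the text does not say which one enters.

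**Conclusion.** The point holds as one about precision. A baseline count of the same kind of event is collected, and the confirmatory NB model does not use it. There is no bias and no type I error problem.

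The benefit of adding it runs from negligible to material: a variance reduction of 0.2% to 42% across the assumed ranges, 4% or less if events are rare with dispersion 1 or below, and about 5% to 24% at 0.4 to 0.8 events per 24 weeks with dispersion 1. These figures assume a rate ratio of 0.6, half to full persistence of each subject's rate, and a recalled count that matches the trial's event definition. The documents supply none of these. Recall error or a different definition would move the gain towards the lower end.

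**What to change.** Before unblinding, in SAP 7.3.2 and Protocol 9.5 (and the matching synopsis text):

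- Add the prior-year exacerbation count as a covariate, for example as 0, 1, 2 or more, or as log(count + 1). Keep surgery, polyp status, treatment, protocol and the offset.
- State which primary-model baseline, CSNS or APOV, enters the NB model, if any.
- Give a missing-count rule so that no subject leaves the analysis, for example a missing category.
- Confirm that Study 3206 records the count in the same way. Its description as identical in objectives and design suggests so but does not establish it. If it does not, keep the current model as primary and run the adjusted one as a sensitivity analysis.

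The cost is one extra parameter (two or three if the count is categorised with a missing level), a small wording change in both documents, and a check across the two studies. No new data are needed from this study.
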